The DIPH job-aids – a set of standardized job-aids (paper forms or web-based interface) corresponding to each of the five steps – are designed to help in the organization and interpretation of data from multiple sectors involved in the delivery of services around the chosen theme using a common data-sharing platform. They are aimed at Woreda leadership and management teams using, inputting and processing data systematically for decision-making, planning and progress-monitoring of the theme.

In Ethiopia, action-research will be employed to adapt, implement and evaluate the DIPH approach in a series of overlapping phases.

1. **Developmental phase (August 2018 – May 2019):** Engage with Ethiopian Federal Ministry of Health and synchronize with similar projects, Adapt DIPH tools and strategies for the local context, and Finalize the selection study area. This phase has been successfully completed, and we anticipate that the study will be implemented in North Shewa zone of Amhara region (12 DIPH, 12 Non-DIPH Woredas).

2. **Implementation phase (August 2019 - July 2021): Implementation for 24 months (two fiscal years: first year for embedding, and second year to establish effectiveness), up to six four-monthly cycles conducted in each of 12 Woredas.**
3. **Evaluation phase (2019 - 2021):** *Process evaluation* to understand and improve on-going implementation issues. *Before-and-after comparison* of intermediate outcomes in intervention and comparison areas via health facility and Woreda surveys.

**Budget:** The estimated cost of DIPH implementation and evaluation will be *will be 10,528,180.01 Ethiopian birr.*

This study is a collaboration between the Ethiopian Public Health Institute (EPHI) and the London School of Hygiene and Tropical Medicine (LSHTM) under the remit of the IDEAS (Informed Decisions for Actions in Maternal and Newborn Health) project. In Ethiopia, we anticipate federal government interest in the findings of the DIPH approach, given its potential to strengthen district level health systems by enabling data-driven decision-making, which could be instrumental in operationalizing the Ethiopian Health Sector Transformation Plan.

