#### **Study Design**

A quasi-experimental study with pre and post comparisons will be applied. Study woredas will be considered as clusters and equal number will be allocated for presence and absence of intervention arm. The study will be conducted in all Woredas of North Shewa Zone by allocating 12 of them in intervention and 12 in non-intervention arms. A matched peer random allocation will be employed. To reduce subjective allocation, matching will be done based on Woredas' performance level and distance.

**Study area:** based on the criteria of a) receptiveness of the zonal health office, B) manageable distance from Addis Ababa, the Amhara region was shortlisted for the implementation phase of DIPH.

Amhara regional state consists of 10 administrative zones, one special zone, 105 Woredas, and 75 urban centres. Amharic is the working language of the state. The capital of the region is Bahir Dar, where Ethiopia's largest inland body of water, Lake Tana, is located. The state of Amhara covers an estimated area of 170,752 square kilometres, and its projected population for 2019 G.C. is 21,844,000.

The study will be implemented in North Shewa, one of the administrative zones in the Amhara region. Geographically, it is bordered in the south and west by the Oromia region, in the north by South Wollo, in the north-east by the Oromia Zone, and in the east by the Afar Region. The total area is 15,936.13 square km, with a population density of 115.30. According to the 2007 census conducted by the Central Statistical Agency of Ethiopia (CSA), this zone has a total population of 1,837,490. 11.66% are urban dwellers. Towns and cities in North Shewa include Ankober, Debre Berhan and Shewa Robit. Amharic is the first language of 92.97% of the population, followed by Oromiffa (6.32%). 94.71% of the population are Ethiopian Orthodox Christians. Details of selected maternal and child-health indicators and health-system infrastructure in the proposed administrative zone are given in Annex I, II and III.

This development phase has been successfully completed, and we anticipate the study will be implemented in all 24 Woredas of the North Shewa zone (i.e. 12 DIPH, 12 non-DIPH).

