**Implementation phase (August 2019-July 2021):** up to six four-monthly cycles of DIPH each will be conducted in the 12 woredas of North Shewa zone over 24 months (i.e. two fiscal years: the first year to complete the embedding of the strategy within the system, and the second year to establish effectiveness).

The Data-Informed Platform for Health will be implemented in the North Shewa administrative zone of the Amhara region. Its Woredas will be stratified by urban and rural, and 12 intervention and 12 comparison Woredas will be randomly selected in collaboration with the zonal health department.

**Embedding:** The Performance Review Team meetings of the district health administration, which is entrusted with integrating planning and facilitating data-driven and collaborative decision-making, will be used as a platform to introduce the DIPH. Activities will focus primarily on:

1. Strengthening the Performance Review Team forum for the engagement of all government and non-governmental stakeholders in order to identify challenges and solutions, and to assess resource allocation and responsibilities. These meetings will be convened with the aim of consensus-building and collective decision-making to improve health systems and services in their areas.
2. Promoting the critical review and regular use of local data to understand health-system progress at the Woreda level.

**Training:** Prior to the initiation of the first DIPH cycle, district health management staff of DIPH Woredas will be provided with three days' intensive residential training based on the specifically-designed curriculum (described above) in their zonal city. On average, six staff members per Woreda will be trained by the research team. Along with the Woreda's health department head, programme officers and an HMIS focal person, experts from the zonal health department will be included in the training. The three-day residential training will be conducted by the DIPH research investigators team

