**Field research team:** Overall, the field team will comprise one DIPH regional coordinator, four DIPH support supervisors and one data manager. The positions of DIPH support supervisor will be filled by applicants who have completed their MPH with a minimum of two years' experience in the Ethiopian health system, while the regional coordinator will have at least 10 years' experience of research coordination. The data manager should have an MSc. in computer programming. Recruitment will be carried out through EPHI in collaboration with IDEAS-LSHTM.

Each support supervisor will be assigned three Woredas where they will provide overall technical support in implementing the DIPH strategy. This will consist of inducting, orientating and handholding Woreda stakeholders during the implementation of the initial cycles, participating in Woredas' monthly performance-review meetings, and monitoring collected data. Data-collection will be performed on tablets using appropriate software for electronic data collection. Data collected from the field will be sent to EPHI's server on a daily basis through the Internet File Streaming System, a technology for transferring data already installed at EPHI.

**Evaluation phase (2019-2021):** This will have three aspects:

- I. **Process evaluation** – to understand and address on-going implementation issues. The monitoring of DIPH in-progress will address the following questions:

1. To what extent is health data used for problem-solving and delivering health services in each DIPH cycle?
2. What is the level of engagement of various health stakeholders?
3. What are the key mechanisms for data-sharing and consensus-building among the range of health-service stakeholders at the Woreda level?
4. What are the facilitators of, and barriers to, sustaining the DIPH strategy?

Data will be collected on structured forms by DIPH support supervisors for each cycle throughout the implementation of DIPH. (Appendix: DIPH Study Instruments, Section B: monitoring framework, definition and indicators). Synthesised findings will be presented periodically to respective Woreda staff so that learning can be used to improve the next cycle.

II. **Before-and-after comparison** of health-system outcomes in intervention- and comparison-district (Woreda) surveys to assess changes resulting from DIPH implementation for at least two fiscal years, in terms of

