#### **Exclusion criteria**

Study participants who do not consent will be excluded.

**Timing:** the baseline study will be conducted in early August 2019, prior to the DIPH-training of Woreda staff, while the end-line survey will be conducted in late July 2021, after the end of the sixth DIPH cycle.

**Study participants:** The survey respondents will be the head of the health department, all programme officers and data managers at the district level. All eligible district staff will be interviewed, except those working in their respective districts for less than six months. We anticipate on average 6 - 7 eligible staff would be available in each Woreda and we aim to include all of them in the study.

Table 1. Sample size for before-vs.-after comparison

Indicator	Expected level at baseline	Expected Minimum percentage point increase	Health management staff assessed/ Woreda	No. of Woredas study arm
Health Information System performance at the district level	50%	25%	6	12

The sample size estimations for the required number of Woredas required per study arm is based on the statistical formula recommended by Hayes et al10. i.e.

$$c = 1 + (z_{\alpha/2} + z_{\beta})^2 \frac{\pi_0(1-\pi_0)/m + \pi_1(1-\pi_1)/m + (k_0^2\pi_0^2 + k_1^2\pi_1^2)}{(\pi_0 - \pi_1)^2}$$

Based on the calculations reported in Table above, a minimum sample size of 72 health management staff per study arm (144 in total) would have 80% power to detect a difference of at least 25 *percentage points* as statistically significant.

Where:-

C is number of clusters required (Woredas)

$Z_{\alpha/2}$  is confidence level (95%)

$Z_{\beta}$  is required power (80%)

$\pi_0$  is true proportion in the absence of intervention (50%)

$\pi_1$  is true proportion in the presence of intervention (75%)

m is individuals sampled in each cluster/woreda (72)

$k_0$  is coefficient of variation of true proportion in the absence of intervention (0.096942)

$k_1$  is coefficient of variation of true proportion in the presence of intervention (0.096942)

Based on the calculations reported in Table above, a minimum sample size of 72 health management staff per study arm (144 in total) would have 80% power to detect a difference of at least 25 *percentage points* as statistically significant.

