## Implementation of DIPH project

No	Activities	19	19	19	19/20	20	20	20/21	21	21	21
	Year	19	19	19	19/20	20	20	20/21	21	21	21
	Months	May	June	Jul-Oct	Nov-Feb	Mar-Jun	Jul-Oct	Nov-Feb	Mar-Jun	July	Aug-Nov
	Developmental phase										
1	Ethics/IRB submission										
2	Baseline survey										
	Implementation phase										
3	DIPH training										
4	DIPH cycles			C1	C2	C3	C4	C5	C6		
	Evaluation phase										
	DIPH cycle Monitoring										
5	End-line survey										
6	Data cleaning, Analysis & reporting										
7	Dissemination										

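### Matched random allocation is not carried into the difference-in-differences model, and the draw is not fixed after the baseline survey

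*Combined protocol and SAP*

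**What the plan says.** **Allocation.** The Study Design section allocates 12 woredas to each arm: "A matched peer random allocation will be employed", and "matching will be done based on Woredas' performance level and distance". The implementation-phase paragraph adds urban/rural stratification and says "12 intervention and 12 comparison Woredas will be randomly selected in collaboration with the zonal health department".

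**Analysis.** The Data Analysis Plan estimates a net effect, the change in DIPH woredas against the change in control woredas. It uses a multilevel regression with districts at level two, adjusted for respondent characteristics and for district contextual factors that it does not list. It names no pair, stratum or matching term.

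**Timing and collectors.** The timing paragraph says "the baseline study will be conducted in early August 2019, prior to the DIPH-training of Woreda staff". No section dates the random draw, and the activity chart has no row for it. The data-collection paragraph gives baseline to the DIPH field teams and endline to an independent recruited team. The field research team includes four support supervisors: "Each support supervisor will be assigned three Woredas where they will provide overall technical support in implementing the DIPH strategy". Four times three is 12, the size of the DIPH arm.

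**The concern.** Matching is worth doing if paired woredas would change alike without the intervention. The estimated net effect then varies less than an unpaired analysis assumes. A model that ignores the pairs reports error bars that are too wide and gives away power that the design has already paid for.

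The order of draw and baseline matters because baseline enters a difference in changes one-for-one. If arms are known at baseline, the people who will later support the DIPH woredas could code them differently, and a different endline team would not repeat that error. Some survey items leave room for this: the two meeting-forum sections of Module V ask the collector to check meeting records and code what was discussed.

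**Working it through.** **1. The plan's own figure.** Inputs from the sample-size section: proportions 0.50 and 0.75, k = 0.096942, two-sided 5%, 80% power, and 6 staff per woreda from Table 1. (The symbol key prints 72 for m, which is the per-arm total.)

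c = 1 + (1.960 + 0.842)² × [0.25/6 + 0.1875/6 + 0.096942² × (0.25 + 0.5625)] / 0.25² = 11.12, rounded up to 12 woredas per arm; 12 × 6 = 72 staff. The plan's figure reproduces. The formula is for an unmatched comparison at one time point.

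**2. Standard error of the net effect on these inputs.** Take separate staff samples at the two surveys, stable woreda levels that cancel in the change, and DIPH at 0.75 at endline with the other three arm-by-survey cells at 0.50:

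SE = √[(3 × 0.25 + 0.1875) / 6 / 12] = 0.1141, or 11.4 points.

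The 25-point target is 0.25 / 0.1141 = 2.191 standard errors. This serves only to compare two analyses of the same data.

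**3. Pairs uncorrelated in change.** Noncentral t gives 55.4% power unpaired (24 − 2 = 22 df, critical value 2.074) and 51.5% paired (12 − 1 = 11 df, critical value 2.201). Pairing costs 3.8 points before rounding.

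**4. Pairs correlated in change.** With correlation ρ the true SE is 0.1141 × √(1 − ρ), but the unpaired test still uses an error term of about 0.1141. Its cut-off is therefore 2.074/√0.7 = 2.48 true SEs at ρ = 0.3 and 2.074/√0.5 = 2.93 at ρ = 0.5. At ρ = 0.3 the true SE is 0.0955, so the target is 2.62 SEs. Simulation of 12 pairs (200,000 runs):

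| ρ | Type I, unpaired | Power, unpaired | Power, paired |
|---|---|---|---|
| 0.3 | 2.1% | 56.2% | 66.4% |
| 0.5 | 0.9% | not needed here | not needed here |

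The two analyses break even near ρ = 0.1.

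**5. Why the term must act on the change.** A pair effect that is the same at both surveys subtracts out of each woreda's change. In balanced data, adding it as a main effect alters neither the net effect nor its standard error. Only a pair-by-time term, or the matching factors by time, removes variation that pairs share in the change.

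**6. Cost of the lighter option.** With performance level, distance and urban/rural each as one term on woreda change, 24 − 1 − 1 − 3 = 19 df remain. If the factors explain nothing and are balanced between arms, power at 2.191 SEs on 19 df is 54.8%, about 0.6 points below 55.4%.

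**7. Order of draw and baseline.** The activity chart lists "Baseline survey" under the developmental phase, and the draw is described under implementation, which suggests baseline came first. But the Summary gives "Developmental phase (August 2018 – May 2019", and baseline is dated early August 2019, the month implementation starts. The order stays open.

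**The case against.** **The pairing loss may be small, and it errs on the safe side.** A conservative test does not threaten validity. The correlation is assumed; no section gives it. The plan's own k also leaves little room for it on the staff-level proportion. With no intervention effect, the between-woreda variance is 0.096942² × 0.25 = 0.00235 per survey, against sampling variance of 0.25/6 = 0.04167. Even if all between-woreda change were shared within pairs, with levels unrelated across surveys, the correlation would be 0.00235 / (0.00235 + 0.04167) = 0.05, below break-even. This stands, and it argues against making strict pairing the only option. It does not settle the matter for the 0-100 indices, which are calculated per woreda and draw partly on office-level records rather than on six independent yes/no answers.

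**The planned adjustment for contextual factors might cover the matching.** It might, but the factors are unnamed and no interaction with time is stated.

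**Stronger readings.** A reader might infer that baseline is biased by arm. That needs the draw to come first, collectors to know the arms, the future supervisors to do the collecting, and coding to differ by arm. The documents do not establish this chain. A collector change common to both arms cancels in the net effect, and an independent endline team is a strength.

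A reader might also infer that the two allocation descriptions conflict. They can be nested: Annex II lists 2 urban and 22 rural woredas, which allows 1 urban and 11 rural pairs. "A quasi-experimental study with pre and post comparisons will be applied" might suggest non-random allocation, but the same section states a random one. The Amhara Health Bureau's role in selecting woredas can mean site selection.

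**Conclusion.** The point holds in two limited parts.

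First, the matching is used to allocate but is not named in the analysis of change. If pairs are positively correlated in change, the consequence is a conservative test and lost power: about 10 points at correlation 0.3, nothing near 0.1, and a gain of about 4 points from ignoring the pairs at zero. These figures assume roughly normal woreda changes and a model whose error term is the woreda-to-woreda variation in change. The standard error comes from the plan's inputs; the correlations do not.

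Second, the plan leaves open whether arms are known when baseline is collected. No size can be put on any resulting error from the documents, and none is claimed. The case for acting is that the estimator passes baseline error straight through and the safeguard costs almost nothing.

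The relation between pairs and strata is a matter of wording only.

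**What to change.** **Data Analysis Plan.** State that the model reflects the matched allocation in the change, by a pair-by-time term or by performance level, distance and urban/rural by time, and choose one before endline data are seen. Strict pairing leaves 11 df and loses about 4 points of power if pairs are uncorrelated; the matching factors by time cost fewer degrees of freedom.

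**Implementation-phase and timing paragraphs.** Add, for example: *Arms are drawn after the baseline survey is complete in all 24 woredas and before DIPH training. Support supervisors are assigned their woredas only after the draw.* The draw must then fit between the early-August 2019 baseline and training for cycle 1, charted July to October 2019. If the draw came first, disclose it and add a sensitivity analysis of the net effect without the collector-coded items.

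**Study Design, wording only.** Say that pairs are formed within urban/rural strata.

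The cost is a few sentences and a tight slot for the draw; no extra data collection is needed.

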1. Health Information System performance at the district level (the summary measure will be created based on the constructs of 1) essential infrastructure for data management, 2) data diversity, 3) reporting timelines, 4) data-quality assessment mechanisms, and 5) data use).
2. Governance of data-driven decision-making at the district level (the summary measure will be created based on the constructs of 1) evidence-based decision-making, 2) participatory decision-making, 3) understanding value of data, 4) health system support for data-use/data-driven decision-making, and 5) accountability).

The summary measures/indices will be calculated for each of the 24 Woredas at baseline and at endline, and will range from 0-100%. They will also be categorized to create indicators to determine proportion change for before and after comparison.

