#### **Inclusion criteria**

- All Woredas in North Shewa zone will be included in the study.
- All managerial and administrative Woreda staff.

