**b) Change in Governance of data-driven decision-making at the district level level as compared to non-DIPH districts .**

It refers to changes in the **organizational** aspects of district health system (information culture, structure, resources, and roles and responsibilities of key contributors at each level of the health system. )

*Key constructs:*

- 1) evidence-based decision-making,
- 2) participatory decision-making,
- 3) understanding value of data,
- 4) health system support for data-use/data-driven decision-making, and
- 5) accountability).

The primary outcomes are the survey-based assessment indices developed by Performance of Routine Information System Management (PRISM) Toolkit (<https://www.measureevaluation.org/resources/publications/tl-18-13/index.html>). They will be created by summing the survey item's responses and converting scores to fall on a standardized scale of 0-100.

Study data will be analysed using descriptive, inferential and regression statistics. Chi-square and t-test will be used to compare sample characteristics between DIPH and non- DIPH study aims to assess the differences in categorical and continuous variables, respectively.

We are using difference-in-differences estimates because the change may inherently happen over time. Therefore, a control group will capture this intrinsic temporal change without DIPH intervention and subtract it from the change brought by the DIPH intervention to assess the net effect on key study outcomes i.e Health Information System performance and Governance of data-driven decision-making at the district level. First, we will calculate absolute differences in percentages from the baseline and the endline, then calculate the net-effect by subtracting the absolute DIPH- intervention difference from the control. We will use multilevel random regression to test the

intervention's impact (net-effect), accounting for observed and unobserved time-invariant and the time-variant factor between intervention and control sites.

We will include districts as level two variables with multilevel modelling to control intra-class correlation. The analysis will be adjusted for personal and professional characteristics of respondents and contextual factors of districts

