### Amhara Health Bureau

The leading role of the Amhara Health Bureau in the DIPH project will be facilitating the project's implementation through selecting Woredas; and, from time to time, participating in field supervision during the project's implementation, enabling them to provide their views and feedback by the end of each cycle.

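### Does the plan need to say how the matched pairs relate to the urban/rural strata, and how 24 clusters enter the difference-in-differences test?

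*Combined protocol and SAP*

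**What the plan says.** Under Study Design, the protocol puts all 24 Woredas of the zone into two arms of 12. It says "A matched peer random allocation will be employed" ("peer" evidently stands for "pair") and that "matching will be done based on Woredas' performance level and distance". Under Implementation phase, the same section says: "Its Woredas will be stratified by urban and rural, and 12 intervention and 12 comparison Woredas will be randomly selected". That sentence does not mention pairs, and the matching sentence does not mention urban or rural status.

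Inclusion criteria says "All Woredas in North Shewa zone will be included in the study". The paragraph on the Amhara Health Bureau gives the bureau the task of facilitating "implementation through selecting Woredas".

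On outcomes, the protocol says "The summary measures/indices will be calculated for each of the 24 Woredas at baseline and at endline, and will range from 0-100" per cent. The Data Analysis Plan estimates a difference-in-differences net effect by multilevel regression: "We will include districts as level two variables with multilevel modelling". It adjusts for respondent characteristics and unlisted contextual features of the districts. It also says that the regression accounts for differences between intervention and control sites, observed or not, both fixed and changing over time. It names no pair, stratum, performance or distance term, and no degrees of freedom.

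**The concern.** Read separately, the two allocation sentences look like two different randomisation schemes. If urban/rural status were in fact ignored, an unrestricted draw of 12 from 24 would put both urban Woredas in the same arm with probability 11/23 = 47.8%. The health bureau's part in choosing Woredas could also suggest that the arms are not purely random.

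On the analysis side, a pair-matched design is usually analysed with its pairs, and with only 24 clusters the reference distribution matters. The pair term, the district covariates and the degrees of freedom are not fixed, so an analyst could settle them after seeing the data. At stake would be the error rate and the power of the test for both primary outcomes.

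**Working it through.** **Allocation.** Annex II lists 2 urban Woredas (Debre Berhan and Shewa Robit) and 22 rural ones. Both counts are even, so 1 urban pair and 11 rural pairs make the 12 pairs, with one Woreda of each pair drawn at random. This meets both sentences at once. Since every Woreda in the zone is in the study and the arms are drawn at random, the bureau's selecting role fits the choice of study area.

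**The plan's own sample size.** Inputs from the sample-size text: proportions 0.50 and 0.75, k = 0.096942 in both arms, two-sided 5%, power 80%, and 6 staff per Woreda (Table 1; 72 per arm / 12).

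- Variance per pair of clusters: 0.25/6 + 0.1875/6 + 0.096942² × (0.25 + 0.5625) = 0.04167 + 0.03125 + 0.00764 = 0.08055.
- c = 1 + (1.960 + 0.842)² × 0.08055 / 0.0625 = 11.12, rounded up to 12. The stated figure reproduces.
- This is the unmatched form, so an analysis that ignores pairs agrees with the way the study was sized.
- Noncentral-t power for 12 per arm, with 0.25/√(0.08055/12) = 3.05: 83.0% on 22 df and 79.3% on 11 df with no gain from matching. These figures belong to a two-cell endline comparison, not to the difference-in-differences analysis.

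**Pairing against not pairing.** t(0.975) is 2.0739 on 22 df and 2.2010 on 11 df. The ratio of interval half-widths, paired over unpaired, is 1.061 × √(1 − ρ), where ρ is the within-pair correlation of Woreda changes. Break-even is ρ = 1 − (2.0739/2.2010)² = 0.112.

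The documents do not give ρ, the staff standard deviation of the index or the correlation r of true Woreda levels between rounds, so these are assumptions. From k, the between-Woreda SD is 4.85 points at 50% and 7.27 at 75%. Assume 6 staff, perfect matching and r from 0 to 0.8. The covariance of changes within a pair is (4.85 × 7.27 + 4.85²)(1 − r).

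Example with staff SD 25 and r = 0:

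- Staff sampling variance of a Woreda mean is 625/6 = 104.2.
- Variance of change is 255.3 (control) and 284.7 (intervention), sum 540.0.
- Twice the covariance is 117.5, so ρ = 0.22.
- Half-width is 2.0739 × √(540.0/12) = 13.9 points unpaired and 2.2010 × √(422.5/12) = 13.1 points paired.

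| Outcome (assumed) | ρ, r = 0 / 0.5 / 0.8 | Unpaired half-width | Paired half-width |
|---|---|---|---|
| Binary | 0.070 / 0.036 / 0.015 | 24.6 / 24.1 / 23.9 | 25.2 |
| Index, staff SD 25 | 0.22 / 0.12 / 0.05 | 13.9 / 13.1 / 12.6 | 13.1 |
| Index, staff SD 15 | 0.43 / 0.27 / 0.13 | 9.9 / 8.8 / 8.0 | 7.9 |

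Imperfect matching moves every case towards a paired interval 6% wider. The table is not a bound in the other direction: many instrument items describe the office rather than the respondent, and with no staff variance at all ρ would be 0.80 to 0.95. The documents therefore do not show which analysis is more precise.

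**Validity if pairs are ignored.** In simulation (12 pairs, t on 22 df) type I error is 5.0%, 4.2%, 2.8% and 1.3% at ρ = 0, 0.07, 0.22 and 0.43. The test is at or below its nominal level.

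**Power for the difference-in-differences at 25 points**, from the variances above, unpaired against paired on useless matches:

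- Binary: 52% to 55% against 49% to 51%.
- Staff SD 25: 95% to 97% against 92% to 96%.
- Staff SD 15: above 99% for both.

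**Fixed Woreda covariates.** In a random-intercept check (assumed Woreda SD 5, Woreda-by-period SD 3, staff SD 15), adding two fixed Woreda features as main effects moved the estimate by 0.00 with 6 staff in every round. With 4 to 8 staff it moved by 0.18 points on average, against a standard error of 3.6.

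**Reference distribution.** A 1.96 cut-off applied to a t statistic gives a true two-sided level of 6.3% on 22 df and 7.6% on 11 df.

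**The case for a change.** The strongest case for a change is that this model tests both primary outcomes, and the open choices could be settled with the data in view. On the plan's two-cell formula the choice between 22 and 11 degrees of freedom gives 83.0% or 79.3%, either side of the intended 80%. A default normal test would be somewhat liberal.

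There is a further point on the random part of the model. If the multilevel model carried only a district intercept, a t reference on 22 df would not by itself repair the standard error. With an assumed Woreda SD of 4.85, staff SD 15 and 6 staff, simulated type I error is 9.4%, 6.7% and 5.0% at between-round correlations of 0, 0.5 and 0.8.

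What stands is that the text is silent on the pair term, on whether covariates enter with period, on the random part for period and on the reference distribution. What does not stand is the step from silence to error. The plan nowhere commits to a normal reference or to an intercept-only model, and its statement about fixed and time-varying site differences leaves room for a Woreda-by-period term. The 83% against 79% contrast does not describe the difference-in-differences analysis. Urban/rural status and distance are fixed features whose main effects cancel or nearly cancel there, so leaving them unnamed costs almost nothing.

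**Conclusion.** No change to the plan follows. The two allocation sentences describe one feasible scheme, 1 urban and 11 rural pairs. The remaining gap is one that an analyst fills sensibly, by comparing Woreda-level changes or fitting a model with a Woreda-by-period term, with a t reference on 22 df, or 11 if pairs are used. Either choice is defensible. Pairing on useless matches costs about 0 to 4 points of power; ignoring useful pairs with the t reference costs precision but not validity.

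These sizes rest on the plan's k and 6 staff per Woreda, and on assumed staff SDs (15, 25 or a binary outcome) and between-round correlations (0 to 0.8). The 6.3% and 7.6% levels, and the 9.4% for an intercept-only model, would arise only from choices the plan does not state. A sentence making the scheme explicit would help readers, but no rule as written gives a wrong result.
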